# Endpoint to address the secondary objective

# Variables required to address the secondary objective

Secondary objective 1: To describe the safety profile of rapidly infused CT-P10 in patients with NHL or CLL in the 6 months post-index date

- Proportion of patients who experience the following safety events in the 6 months post-index date, and frequency of each per patient per month:
  - Any IRR.
  - Any grade 3 or grade 4 IRR (according to the Common Terminology Criteria for Adverse Events [CTCAE] version 4).
  - Any other AE (excluding IRR).
  - Any other grade 3 or grade 4 AE (excluding IRR).
  - o Any serious adverse event (SAE).
- Proportion of patients with AEs as the primary cause for treatment discontinuation.
- Summary distributions of event type by grade.
- Proportion of all rapid CT-P10 infusions during which IRRs were experienced.

For all AEs (temporally associated with CT-P10 treatment) during the 6 months post-index (including the index date):

- Description of AE
- IRR (Yes/No)
- Event start date
- Event end date
- Seriousness
- CTCAE v4.0 grade
- Clinician's assessment of relationship to CT-P10
- AE resulted in treatment discontinuation (Yes/No).

Secondary objective 2: To describe the clinical effectiveness of rapidly infused CT-P10 in patients with NHL or CLL in the 6 months post-index

- OS, defined as the time from the index date until death from any cause.
- Proportion of patients surviving at six months following NHL or CLL diagnosis and following the index date.
- PFS, defined as the time from the index date until the first documented evidence of disease progression or death from any cause.
- Proportion of patients surviving and free from disease progression at six months following the index date.
- Summary of best response to CT-P10

- Date of data collection.
- Patient alive at 6 months post-index (Yes / No / Not known)?
- If no, date of death (DD/MM/YYYY).
- All treatment response assessments in the post-index period (date, recorded treatment response [complete response / partial response / no response or stable disease / progressive disease], assessment based on IWCLL / Revised Response Criteria for Malignant Lymphoma / local criteria / other criteria, type(s) of

- (complete response / partial response / no response or stable disease / progressive disease).
- Proportion of patients achieving a complete or partial response.

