- Time to complete or partial response, defined as the number of days from the index date until first documentation of complete or partial response by the local investigator.
- assessments used to evaluate response).
- Date (within 6 months post-index) of last recorded hospital visit.

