# Secondary objective 3: To describe treatment patterns in patients with NHL or CLL who receive treatment with rapidly infused CT-P10.

- Summary measures of the following CT-P10 treatment parameters:
  - Number of infusions
  - o Duration of infusions
  - Starting and subsequent doses
  - Chemotherapy regimen given with CT-P10 (if applicable) and premedications received
  - o Time on treatment
  - Reason why treatment was discontinued (if applicable)
- Distribution of subsequent treatment regimens (after discontinuation of CT-P10).

- For CT-P10 treatment (in the post-index period):
  - o Date of each infusion.
  - Pre-medications given.
  - Treatment doses given (actual and per m²).
  - o Duration of each infusion.
  - Name of chemotherapy regimen given with CT-P10.
  - Treatment discontinuation date (the date of discontinuation will be defined as the date of the last dose / infusion) or ongoing.
  - Treatment ongoing at 6 months post-index (Yes / No / not known).
  - Reason for permanent discontinuation (adverse event, death, disease progression, completed course of treatment, budget constraints, other).
- Name, type and start date of subsequent treatment regimens (after discontinuation of CT-P10).

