#### 9.7.2 Secondary analyses

For the secondary endpoint safety analyses, rates of events per-patient-per month will be reported. Secondary clinical effectiveness endpoints will be reported separately for patients with NHL or CLL. The time-to-event clinical effectiveness endpoint analyses (OS, PFS, time to complete or partial response) and CT-P10 treatment duration will be displayed descriptively using Kaplan Meier plots from the index event until the date of the event or censoring. Patients who are known to be alive at 6 months post-index will be censored on that date for OS whereas patients who are lost to follow-up will be censored at the date they were last known to be alive (i.e. the last recorded hospital visit within the 6 months post-index). For PFS, patients will be censored on the date they were last known not to have disease progression (i.e. the date of last documented response assessment) and for time to complete or partial response, patients will be censored at the date of the last recorded known response. For treatment duration, censoring will occur at the 6 months post-index date (if CT-P10 treatment is known to be ongoing at 6 months) or the date of the last infusion (if the patient is lost to follow-up). Absolute counts and the percentages of these events occuring in each disease indication group will be reported. Survival rates for 6 months post NHL or CLL diagnosis will also be calculated. Summary data will be tabulated and also displayed graphically where appropriate.

The proportion of patients assessed as having a best response of complete response, partial response, stable disease or progressive disease within the 6 months post-index based the documented assessment of the local investigator and the proportion of patients with a complete or partial response, will be presented with 95% CI.

For the demographic, clinical, and NHL/CLL disease characteristics endpoint analyses, the study population will be described by means of summary statistics. Distributions and descriptive statistics of both central tendency (medians and means) and dispersion (standard deviation, interquartile range [IQR]) will be presented for

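### Best response, CR/PR proportion and time to response have no cut at the start of a subsequent regimen, so a response reached on later treatment can be credited to CT-P10

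*Protocol*

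**What the plan says.** Four parts of the protocol bear on this. The SAP is not among the documents reviewed.

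- **Label (section 9.3, secondary objective 2).** One endpoint is "Summary of best response to CT-P10". The next is "Proportion of patients achieving a complete or partial response", with no reference to the regimen in use.
- **Data collected (section 9.3, secondary objective 2).** The variable list asks for "All treatment response assessments in the post-index period", each with its date and recorded response.
- **Derivation.** Section 9.7.2 reports the proportions with a best response of CR, "partial response, stable disease or progressive disease within the 6 months post-index based the documented assessment of the local investigator", together with the CR/PR proportion. Section 9.3 runs time to response from the "index date until first documentation of complete or partial response by the local investigator". Section 9.7.2 then fixes the censoring: "for time to complete or partial response, patients will be censored at the date of the last recorded known response".
- **Later treatment (section 9.3, secondary objective 3).** The protocol collects "Name, type and start date of subsequent treatment regimens (after discontinuation of CT-P10". Progression and adverse events are among the listed reasons for permanent discontinuation. The start date of the next regimen is used only to describe treatment patterns.

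The definition of CR and PR in section 2.2 refers to published or local criteria and not to the treatment being given. Section 9.7.4 plans no sensitivity analysis.

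**The concern.** The label attributes the response to CT-P10, but the derivation does not carry that attribution out. The protocol expects some patients to stop CT-P10 and start another treatment, and the 6-month window keeps running after they do.

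Two kinds of patient are affected:

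- A patient with no CR/PR on CT-P10 who reaches one on the next regimen within 6 months becomes a responder, with a time to response.
- A patient with a PR on CT-P10 that becomes a CR on the next regimen is reported with a best response of CR. The CR/PR proportion and time to response do not change for this patient.

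At stake is the meaning of three secondary effectiveness endpoints. They are reported separately for NHL and CLL, so a handful of patients can move the figure in the smaller CLL group.

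**Working it through.** **Rule applied to one patient.** Suppose disease progresses on CT-P10 at month 2, a new regimen starts, and CR is documented at month 5.

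| Endpoint | Rule in the protocol | Result |
|---|---|---|
| PFS | first documented progression or death | event at month 2 |
| Best response | best assessment in the 6 months after index | CR |
| CR/PR proportion | any CR or PR in the window | responder |
| Time to response | index to first documented CR/PR | about 5 months |

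The same patient is a progression at month 2 and a complete responder to CT-P10. No rule in sections 2.2, 9.3 or 9.7.2 prevents this.

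**Direction.** With the patients analysed held fixed, adding assessments cannot lower a best response or remove a responder, so those two figures can only rise. Time to response differs. A later response adds an event at a late time, which can lengthen the time among responders. It also keeps the switcher at risk as a non-responder until that date, where a cut would have censored the patient earlier. The Kaplan-Meier curve can therefore move either way.

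**Size.** The protocol gives no figure for this effect, so there is none to reproduce. The group sizes come from section 9.5: 76,800 + 20,200 = 97,000; 300 × 76,800 / 97,000 = 237.5 and 300 × 20,200 / 97,000 = 62.5, which agrees with the stated split of about 240 NHL and 60 CLL.

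The inflation of the CR/PR proportion is s × r, where

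- s = share of patients who start a new regimen within 6 months with no CR/PR before it;
- r = share of those who reach CR/PR on that regimen inside the window.

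Neither is in the documents. The values below are assumptions.

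| s | r | s × r (points) | NHL patients (240 × s × r) | CLL patients (60 × s × r) |
|---|---|---|---|---|
| 2% | 30% | 0.6 | 1.4 | 0.4 |
| 5% | 50% | 2.5 | 6.0 | 1.5 |
| 10% | 50% | 5.0 | 12.0 | 3.0 |
| 15% | 70% | 10.5 | 25.2 | 6.3 |

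For scale, at an assumed response proportion of 50% the exact 95% CI is 43.5 to 56.5% with 240 patients (half-width (56.5 − 43.5) / 2 = 6.5 points) and 36.8 to 63.2% with 60 patients (half-width (63.2 − 36.8) / 2 = 13.2 points). The 5% and 50% case lies well inside both half-widths. The top case exceeds the NHL half-width but not the CLL one.

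The formula does not cover a PR raised to CR. That shift affects only the split between CR and PR in the best-response table.

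**The case against.** **The collection line is not an analysis rule.** The entry asking for every assessment sits in a list of variables to capture, and full capture is what an analysis tied to CT-P10 would need. This is right. The point therefore rests on the window and censoring in section 9.7.2 and the time-to-response definition in section 9.3.

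**The label already excludes later regimens, and the SAP can supply the cut.** Section 9.7 defers detailed methods to a SAP, and a natural reading of a best response to CT-P10 leaves out a response to salvage treatment. This stands in part: the intention is visible. But the label covers best response only. The protocol also fixes the response window and an endpoint-specific censoring date itself, and a SAP that followed those rules faithfully would credit the later regimen.

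**The failure is not hidden.** A reader might infer that the later treatment erases the CT-P10 failure. It does not. The patient remains a PFS event and is not progression-free at six months, and the discontinuation reason and next regimen are reported.

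**The effect may be small.** It needs failure or stopping, a new regimen, reassessment and response, all within 6 months. Section 9.9 expects progression to be found later than in a trial, which makes the sequence less likely. This stands, and it limits the weight of the point.

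**Conclusion.** The point holds as a gap between the attribution in section 9.3 and the derivation in sections 9.3 and 9.7.2. Taken literally, the rules can credit CT-P10 with a response reached on a later regimen.

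The illustrative range of 0.6 to 10.5 points rests wholly on the assumed switching and response shares. The documents support no single value, and a small effect is plausible.

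Two stronger conclusions might be inferred and are not supported. One is that the response endpoints no longer measure CT-P10: patients who never switch are unaffected, and those already in CR/PR before switching are unaffected for the CR/PR proportion and time to response. The other is that all three endpoints are biased in CT-P10's favour: this is true of best response and the CR/PR proportion, but not necessarily of time to response.

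The endpoints are secondary and descriptive, and section 8.2 states no hypothesis. The correction is worth making because it is cheap and removes an internal inconsistency.

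**What to change.** In sections 9.3 and 9.7.2, and in the SAP:

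1. For best response, CR/PR proportion and time to response, count only assessments dated on or before the start of the first subsequent regimen.
2. For time to response, censor a patient who switches without a prior CR/PR at the last assessment before that start date.
3. Report patients with no assessment before the new regimen as not evaluable for response and give their number, in line with the available-data rule in section 9.7.3.
4. Report how many patients started a new regimen within 6 months, by disease.

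The cut belongs at the start of the next regimen and not at CT-P10 discontinuation. Section 9.3 dates discontinuation at the last infusion, so a cut there would drop end-of-treatment assessments. OS stays as it is.

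The cost is a few sentences and no new data, because assessment dates and regimen start dates are already collected. The downside is a slightly lower reported response rate and possibly a few patients not evaluable.

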## 9.2 Setting

#### 9.2.1 Study population

The source population for this study is adult patients with NHL or CLL who received treatment with rapidly infused CT-P10 as part of their standard clinical care in five European countries.

Patients fulfilling the following criteria will be potentially eligible for inclusion in the study:

- Patients with a confirmed diagnosis of NHL (follicular lymphoma [FL] or diffuse large B-cell lymphoma [DLBCL]) or CLL.
- Patients who had received rapidly infused CT-P10 for their second or a subsequent treatment cycle; 'rapidly' defined as 90-minutes or less.
- Patients at least 18 years of age at the date of diagnosis of NHL or CLL.
- Patients (or next of kin, if appropriate locally) providing written informed consent for study data collection (if this is required according to local country regulations).

Patients fulfilling any of the following criteria will be excluded from the study:

- Patients who had received reference rituximab for any previous treatment cycles
   (i.e. prior to the index event) within the same line of treatment.
- Patients whose medical records are unavailable for review.

As only limited exclusion criteria will be applied, and patients will be included from a range of centres in five European countries, it is expected that the study population will be representative of the overall source population.

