# Secondary objective 4: To describe the baseline demographic, clinical and disease characteristics of patients with NHL or CLL who receive treatment with rapidly infused CT-P10.

Demographic and clinical characteristics (at index date unless specified)

- Summary measures of patients' age, sex, ethnicity, employment status, comorbidities (Charlson Comorbidity Index ), disease duration and prior chemotherapy and rituximab exposure.
- Number of other diagnosed malignancies.
- Summary of Eastern Cooperative Oncology Group (ECOG) performance status at closest time point prior to the index date.
- Summary measures of duration of CT-P10 infusion(s) given prior to the index event.
- Proportion of patients who experienced IRRs with CT-P10 infusion(s) given prior to the index event (by IRR grade).

- Month and year of birth
- Index date
- Date of diagnosis of NHL or CLL
- Sex (male/female)
- Ethnicity
- Employment status (full time / part time / unemployed / student / retired / home-maker) at closest time point prior to index date and date documented.
- Relevant comorbidities ongoing at index date (components of Charlson Comorbidity Index will be captured)
- Prior treatment regimens for NHL or CLL from diagnosis of NHL or CLL to the index date (name and type of treatment, start date, stop date [for

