# most recent regimen and most recent rituximab only]).

- Other malignancies diagnosed prior to the index date.
- ECOG score at closest time point prior to the index date and date of assessment.
- Date and duration of any CT-P10 infusion(s) given prior to the index event and description / CTCAE v4 grade of any IRRs experienced.

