#### 9.7.3 Missing data

Where data are missing from the original medical record, the affected analyses will be conducted using only the results of those patients with data available and the number included in each analysis will be stated.

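### Response is counted from the index date, but response status at index is not collected, so patients already in remission count as achieving response afterwards

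*Protocol*

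**What the plan says.** Protocol Section 9.2.1 admits "Patients who had received rapidly infused CT-P10 for their second or a subsequent treatment cycle". It sets no upper limit on the cycle, does not require active disease, and does not exclude patients already in complete or partial response (CR/PR).

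Under secondary objective 2, Section 9.3 collects "All treatment response assessments in the post-index period". Three endpoints rest on these assessments: best response to CT-P10, "Proportion of patients achieving a complete or partial response", and time to response, "defined as the number of days from the index date until first documentation of complete or partial response by the local investigator".

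For the period before index, secondary objective 4 lists "Prior treatment regimens for NHL or CLL from diagnosis of NHL or CLL to the index date" (names, types and dates) and "Date and duration of any CT-P10 infusion(s) given prior to the index event and description / CTCAE v4 grade of any IRRs experienced". It also lists stage at diagnosis and near index, prognostic scores, LDH, tumour size and number of sites. No item records a response category or remission status at index.

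On analysis, Section 9.7.2 uses Kaplan-Meier plots and says that "for time to complete or partial response, patients will be censored at the date of the last recorded known response". The same sentence censors progression-free survival (PFS) at the last documented response assessment. The response proportion is given with a 95% confidence interval. Under Section 9.7.3, where records are incomplete, "the affected analyses will be conducted using only the results of those patients with data available", and the number analysed is stated.

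**The concern.** Treatment before index is built into the design: every patient enters at the second cycle or later, and the protocol expects earlier CT-P10 infusions. Some patients may already be in CR or PR when the clock starts. If that response is written down again after index, the patient counts as achieving response, and the recorded time to response reflects only when the next assessment was scheduled.

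The response rate, best response and time to response would then depend partly on how late in a course each site switched to rapid infusion. A reader could not separate responses reached after index from responses merely carried past it.

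A statistical analysis plan cannot repair this from the planned dataset, because it cannot condition on a variable that was not captured. Section 9.3 presents its list as the variables to be collected for the objectives, and Section 10 limits collection to what the planned analyses need. Section 9.9 mentions upward bias only for PFS. Section 9.7.4 plans no sensitivity analysis, and its listed subgroups include neither index cycle nor response at index.

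**Working it through.** **Inputs.** Section 9.5 expects about 240 patients with NHL and 60 with CLL. The prevalence figures there give 300 × 76,800/97,000 = 237.5 and 300 × 20,200/97,000 = 62.5, which agrees. The protocol states no expected response rate or time to response, so there is no figure to reproduce. The following are assumptions:

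- q, share already in CR/PR at index: 10% to 50%
- r, response rate after index in the others: 40% to 60%
- c, probability that an existing response is documented again after index: 80% to 100%

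**Response proportion.** Reported rate = qc + (1 − q)r, so the excess over r is q(c − r).

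| q | r=60%, c=100% | r=60%, c=80% | r=40%, c=100% | r=40%, c=80% |
|---|---|---|---|---|
| 10% | 64% (+4) | 62% (+2) | 46% (+6) | 44% (+4) |
| 20% | 68% (+8) | 64% (+4) | 52% (+12) | 48% (+8) |
| 30% | 72% (+12) | 66% (+6) | 58% (+18) | 52% (+12) |
| 50% | 80% (+20) | 70% (+10) | 70% (+30) | 60% (+20) |

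The sign depends on c against r. With q = 30%, r = 60% and c = 50%, the shift is 0.30 × (50 − 60) = −3 points.

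**Against the planned precision.** Take q = 20%, r = 60%, c = 100%. The reported 68% has an exact 95% interval of 61.6% to 73.8% at n = 240, which excludes 60%, and 55.0% to 79.7% at n = 60, which does not. Of the patients credited with a response, 0.20/0.68 = 29% were already in response at index.

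**Time to response.** For the share q, the event time is the gap from index to the next assessment. This follows from the definition and needs no assumption beyond q being above zero.

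**Progression or death before response.** This affects only the Kaplan-Meier curve. Let F be the 6-month cumulative incidence of response and d the share who progress or die first, with constant hazards. If those patients are censored, 1 − KM = 1 − (1 − F − d)^(F/(F + d)).

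- F = 60%: d = 5%, 10%, 20% gives 62.1%, 64.4%, 70.1% (excess 2.1, 4.4, 10.1 points)
- F = 40%: the same d gives 41.2%, 42.6%, 45.7% (excess 1.2, 2.6, 5.7 points)

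**Denominator.** Only patients with no assessment drop out. If 5% of 240 (12 patients) died unassessed and 144 responded, the available-case rate is 144/228 = 63.2%, against 144/240 = 60.0%. The 5% and the 144 are assumed.

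**The case against.** The best counter-argument concerns what is being estimated. The protocol summarises best response to CT-P10, and Section 9.2.1 excludes patients given reference rituximab earlier in the same line. A patient who responded during earlier CT-P10 cycles of that line and is still in response after index has responded to a CT-P10-containing course. Restricting the analysis to patients not yet responding would select slow or resistant disease and understate response to the course. This stands: r is not the one true rate, and the overall figure has a legitimate use. It does not rescue time to response from index, which has no sensible meaning for someone already responding.

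Several stronger readings are tempting, and the documents do not support them:

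- A reader might infer that never-responders have no censoring date. Section 9.3 lists no response or stable disease, and progressive disease, among the recorded response categories, so an assessed never-responder does have one. The wording is loose, not unworkable.
- A reader might infer that the censoring rule inflates the response rates too. It affects only the time-to-response curve, and not even that if no non-responder is censored before the last response.
- A reader might infer that patients who progress are dropped from the response rate. A documented progression is itself a recorded response, so only unassessed patients are lost.
- A reader might take the inflation to be q(1 − r). That holds only if every existing response is documented again.
- A reader might think that the gap is permanent. The charts remain, and patients can be traced through site logs; it is the planned dataset that lacks the item. Stage, tumour size and earlier infusion dates are partial proxies.

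Two further points are fair. Section 9.9 already says that response timing is not uniform and calls the findings real-world estimates, though it is silent on response at index. Competing-risk methods and denominators are normally settled in the statistical analysis plan, so those parts are suggestions for that document.

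**Conclusion.** The point holds for the missing response status at index. Time to response is uninterpretable for patients already in CR/PR, and the response rate and best response mix responses reached before and after index. The expected direction for the response rate is upward provided that c exceeds r, which is plausible but not shown. The size cannot be derived from the documents: over the assumed ranges the excess runs from 2 to 20 points at r = 60% and from 4 to 30 points at r = 40%.

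The censoring wording, competing events and unassessed deaths are lesser matters. These are secondary endpoints in a descriptive study without a hypothesis, and the primary endpoint, infusion-related reactions after the index infusion, is unaffected. The change should be made, but the study does not depend on it.

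**What to change.** - Add to the electronic data collection form the last response assessment before index (date and category). Section 9.2.3 already has each chart reviewed from diagnosis, so this is one item within a period being abstracted anyway. Adding it after data collection would mean returning to the charts.
- Report time to response only in patients not in CR/PR at index.
- Report response rate and best response by status at index beside the overall figure. Show patients already responding as maintained, improved or lost.
- In Section 9.7.2, censor time to response at the last documented response assessment, the term already used for PFS. Show cumulative incidence with progression and death before response as competing events.
- Report the response proportion also with patients who died unassessed kept in the denominator.

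The cost is one data item and some analysis wording. The main drawback is smaller denominators: with 60 CLL patients, q of 10%, 20%, 30% or 50% leaves 54, 48, 42 or 30 for time to response. Some charts may hold no assessment before index, so a category for unknown status is needed.
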